## ABSTRACT

**Background:** Obesity is a chronic disease and is an established risk factor for other chronic diseases and mortality. Young adulthood is a period when people may be highly amenable to healthy behaviour change, develop lifelong healthy behaviours, and when primary prevention of obesity may be most feasible. Interventions in early adulthood have the potential for primary or primordial prevention (i.e., preventing risk factors before disease onset). The primary objective of this study is to determine the feasibility of a 6-month behavioural and educational intervention to promote healthy behaviours for obesity prevention among young adults.

**Methods:** This is the study protocol for a pilot randomized controlled trial. Young adults (age 18-29) attending McMaster University, Hamilton, Canada, will be recruited and randomized to either the intervention or control. The intervention will include individual motivational interviewing sessions (online or in-person) with a trained interviewer plus educational materials (based on Canada's food guide and physical activity recommendations). The control group will receive educational materials only. The primary feasibility outcomes that will be evaluated as part of this pilot study include enrollment, retention ( $\geq 80\%$ ), data completion ( $\geq 80\%$  of weights measured, and surveys completed), and participant satisfaction. Secondary clinical outcomes will include body mass index (BMI) change from baseline to 6-months, physical activity, nutrition risk, health-related quality of life mental health and economic outcomes. Outcomes will be measured remotely using 'smart' electronic scales, activity trackers, and online questionnaires at baseline and every 2 months. Risk stratification will be applied at baseline to identify participants at high risk of obesity (e.g., due to family or personal history). Exit questionnaires will collect data on how participants felt about the study and cost analysis will be conducted.

**Discussion:** Our pilot randomized controlled trial will evaluate the feasibility of an obesity prevention intervention in early adulthood and will inform future larger studies for obesity prevention. The results of this

study have the potential to directly contribute to the primary prevention of several types of cancer by testing an intervention that could be scalable to public health, post-secondary education, or primary care settings.

**Trial Registration:** ClinicalTrials.gov Identifier: NCT05264740. Registered March 3, 2022,

<https://clinicaltrials.gov/ct2/show/NCT05264740>

**Keywords:** Obesity; prevention; young adults; health behaviours; intervention; motivational interviewing

## BACKGROUND

Obesity is a chronic disease, and it is also a risk factor for other chronic diseases. In Canada, the prevalence of obesity among adults was 28% in 2018.(1,2) It has been estimated that the direct costs of overweight and obesity in Canada were \$6 billion annually in 2006.(3) By 2025 approximately 20% of adults worldwide will have obesity.(4) Obesity is defined as a body mass index (BMI)  $>30$  with classes of obesity severity defined as Class 1 (30-34), Class 2 (35-39) and Class 3 ( $\geq 40$ ). Although there are limitations in the use of BMI cut points to define obesity, BMI is strongly correlated with body fat and remains the most practical measure for population-based studies.(6,7) Obesity severity is important, with more severe obesity conferring a substantially greater risk of cancer, other chronic conditions, and poor mental health.(8–10) Obesity is a complex disease with a broad range of socio-ecological risk factors. Obesity treatment is challenging, and primary and secondary prevention interventions are urgently needed to reduce the incidence of obesity and decrease or maintain obesity severity.(11)

The COVID-19 pandemic had a profound impact on activities of daily life, and many causes of weight gain, including chronic stress and physical inactivity, increased during the pandemic. Early indications suggest that 20-48% of people reported weight gain during the pandemic.(12–19) Some reasons include changes in food intake (increased food insecurity, and consumption of “comfort” foods), decreased physical activity, increased sedentary time, and increased alcohol. There is some evidence of sex differences (greater weight gain in women) and increased weight gain among people with higher BMI pre-pandemic.(12,13) One small U.S. study found that pandemic shelter-in-place orders were associated with an average weight gain of 1.5 lbs per month.(20) It is established that obesity can develop slowly over time or as a result of a rapid weight gain.(11) Thus, it is important to investigate interventions that may contribute to modifying health behaviours for obesity prevention.

Young adulthood is a period when people may be highly amenable to healthy behaviour change, develop lifelong healthy behaviours, and when the primary or secondary prevention of obesity may be feasible. Interventions in young adults have the potential for primary cancer prevention (i.e., stopping cancer risk factors before they develop). Young adulthood is a time when weight gain may occur rapidly(21) and developing healthy behaviours is critical to maintaining a healthy weight throughout adulthood. On average, Canadian adults gain 0.5 to 1 kg every two years and this is greater among young adults and those with higher BMI.(22) Systematic reviews suggest that students attending post-secondary education may experience greater weight gain.(23,24)

Narrowly defined lifestyle interventions for obesity prevention, such as those addressing only physical activity, have had limited success.(25) The 2020 Obesity Clinical Practice Guidelines recommend moving “*beyond simplistic approaches of “eat less, move more,” and address the root drivers of obesity*”.(11) Yet, there have been relatively few attempts to implement tailored, population-based obesity prevention interventions in young adults. Obesity interventions must be flexible to address the complex causes of obesity and motivational interviewing may be a successful strategy.(25) Motivational interviewing (MI) is defined as “*a collaborative conversation style for strengthening a person’s own motivation and commitment to change*”.(26) Health care professionals have successfully used motivational interviewing for patients to set personalized goals for successful healthy life changes.(27) Motivational interviewing has shown some success for weight loss interventions in young adults,(25) but it has not been widely implemented for obesity prevention. It is unknown whether obesity prevention interventions are more successful among people at highest risk. Several obesity risk stratification tools have been developed and validated that identify young adults who are at greatest risk of obesity later in adulthood.(28–30) The use of these risk prediction tools to identify young adults who may benefit the most from an obesity prevention intervention may improve success and support broader population-level, precision public health or clinical interventions.

**The primary study objective is:**

1) To determine the feasibility (enrollment, retention, data completion, satisfaction) of a 6-month behavioural and educational intervention to promote healthy behaviours for obesity prevention among young adults.

The **secondary objectives are:**

2) To determine the effects of the 6-month behavioural and educational intervention, compared to an educational intervention only, on change in BMI, health behaviours (nutrition, physical activity and sedentary time), health-related quality of life, and mental health (depression and anxiety).

3) To explore whether obesity risk stratification tools identify young adults who may be more successful in an obesity intervention.

## **METHODS**

### ***Study Design and Population***

We will conduct a pilot randomized controlled trial (RCT). The protocol is reported following the SPIRIT guidelines for RCT pilot studies,(31) the Template for Intervention Description and Replication (TIDieR) checklist and guideline,(32) and has been pre-registered (ClinicalTrials.gov Identifier: NCT05264740). Study participants will be young adults (age 18-29) who are students at McMaster University, Hamilton, Ontario, Canada.

Recruitment posters will be posted in common areas on campus, shared on social media, and through email lists. The study website is available at: <https://motivate.healthsci.mcmaster.ca/>

The study inclusion criteria are:

- English speaking, and capable of providing informed consent.
- McMaster University students 18-29 years of age.
- BMI of at least 18.5 (BMI< 18.5 is considered underweight and will be excluded).
- Access to wireless internet (WiFi) at home.

Exclusion criteria are:

- Physical and mental health conditions that would be contraindications for a weight management intervention, including eating disorders, pregnancy, cancer, or medications that affect body weight.

### ***Randomization***

Participants will be randomized to intervention and control arms in a 1:1 allocation ratio using a computer-generated randomization list that will be generated centrally by the Biostatistics Unit at St Joseph's Healthcare Hamilton. Randomization will be stratified by sex and BMI (BMI<25 vs BMI≥25) to achieve some prognostic balance. We will use permuted blocks of random sizes to ensure equal numbers in each group. The block sizes and allocation will be concealed from the participants and trial staff, and the randomization codes will only be revealed after the participants have been recruited and baseline data has been collected. This is an open-label trial. Trial staff and participants will not be blinded to the intervention, but data analysts will be blinded.

### ***Consent and Ethics***

Ethics approval was obtained from the Hamilton Integrated Research Ethics Board on July 25, 2022 (HiREB Project Number: 14675). Informed consent will be obtained from all participants at the first in-person visit. Participants may choose to withdraw from the study at any time and when possible, we will capture the reasons for withdrawal. Consideration has been given to issues of equity (advertisement and recruitment materials, research staff and investigators) and among this population of students, we do not anticipate that the English-language requirement will be a barrier.

### ***Timing of Visits, Intervention and Control Groups***

An overview of the study design is provided in Figure 1. The first visit will occur in-person with a research assistant to obtain consent, collect baseline measures, provide participants with the study materials/equipment, and build a relationship with the study participants. For all subsequent visits, participants will have the option of in-person or virtual sessions.

The intervention will include motivational interviewing sessions with a trained research assistant/interviewer plus educational material. The motivational interviewing sessions will occur at baseline and once a month (7 visits in total). For this feasibility study, *a priori* criteria for the discontinuation or modification of the allocated intervention are not available.

The research assistant will receive training in motivational interviewing. Intervention fidelity (adherence to the principles of MI) will be assessed using recorded training interviews and established rating scales with continuing training as needed.(33) For training purposes, mock interviews conducted between members of the research team will be recorded and evaluated. Interviews with study participants will not be recorded.

The control group will receive educational material only. The same educational material will be provided to both the intervention and control group and will consist of evidence-based recommendations based on Canada's food guide(34) and Canadian 24-hour movement guidelines.(35) The SPIRIT schedule of enrolment, interventions, and assessments for this study is provided in Figure 2.

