study office once a month to conduct a self weigh-in using a Fitbit electronic ‘smart’ scale (e-scale). They will be asked to weigh themselves monthly and reminders will be sent by email or text message. E-scales are feasible and valid for research conducted remotely and participant adherence to home weigh-ins is high(37–39), as part of this feasibility study we will assess the adherence to self weigh-ins when the scale is located in a private study office. Other secondary outcomes will include nutrition risk, physical activity (measured as 24-hour movement, including sedentary time and sleep), and mental health collected using online questionnaires at baseline and every 2 months. Nutrition risk will be measured using the National Cancer Institute's Dietary Screener Questionnaire (DSQ). The DSQ measures the frequency of intake of selected foods that are known to affect risk of cancer and obesity, including fruits, vegetables, whole grains, and sugary drinks. The DSQ has good validity compared to 24-hour recalls.(40) Self-reported physical activity, sedentary time, recreational screen time and sleep will be measured to describe adherence to recommended 24-hour movement guidelines using questionnaires previously used in young adults(41), including the International Physical Activity Questionnaire (IPAQ)(42), and International Sedentary Assessment Tool (ISAT).(43) The Insomnia Severity Index will also be included as a measure of perceived sleep quality.(44) Mental health is an important upstream determinant of health behaviours and is highly associated with obesity risk. We will measure depressive symptoms, anxiety and health-related quality of Life using the following validated tools: Centre for Epidemiologic Studies Depression Measure -10 (CESD-10)(45), Generalized Anxiety Disorder -7 (GAD-7)(46), and Euroqol-5D-5L (EQ-5D-5L).(47) We anticipate that some youth may also raise issues related to alcohol or substance use in the interviews, thus we have included questions that ask about alcohol, smoking, cannabis and medication use in the questionnaires. A single-item measure of body satisfaction is included in the study to evaluate any changes over the course of the study.(48) A validated two-item food insecurity screen is also included.(49)

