#### ***Data collection and management***

All data will be stored in a secure REDCap database. Surveys will be collected online using secure electronic data capture in REDcap. The final trial dataset will only be available to select members of the research team (LA, LM, TI). The final dataset will not be made publicly available to protect the confidentiality of participants, but de-identified data could be made available upon request. Baseline surveys will collect detailed data on socioeconomic variables, including age, sex, gender identity, income, and food security, medical history, and the secondary outcomes described above (nutrition, physical activity, sedentary time, mental health). Follow-up surveys administered every 2 months (at 2, 4 and 6 months) will collect updated data on secondary outcomes. Participants in both the control and intervention groups will receive a \$30 gift card at the time of each survey completion. We will continue to collect data from participants if they deviate from protocol unless there is withdrawal from the study. To ensure confidentiality, a unique study id number will be used for the weight and activity data and linked at McMaster by the research team to the main study database.

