#### ***Safety protocols and unanticipated outcomes***

Possible adverse outcomes may include concerns related to mental health, including eating disorders, or frustration due to weight gain/no change. Expectations of the research will be laid out before enrollment and feelings such as these can be addressed as part of the motivational interviewing process. Our research team including the research assistants/interviewers and physician co-investigator (EA) are equipped to assess the situation and provide necessary referrals. Medical and counselling services are available on campus for all

students. If participants raise any concerns of self-harm or harm to others, then safety protocols will be followed.

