### ***Sample size***

Our sample size estimation was based on feasibility considerations and calculated using WINPEPI.(53) Using a 95% confidence level, assuming that 80% of the participants will complete the study with a 7.5% margin of error, 110 participants are needed (55 intervention and 55 control). This sample size is not sufficiently powered to make between-group comparisons but will provide accurate data on feasibility and estimates of effect size variability that will inform the sample size calculation of a larger definitive trial.

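### Eating disorders are an entry contraindication and a foreseen adverse outcome, but no rule pauses interviews, weigh-in prompts or tracker wear if one emerges after randomization

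*Combined protocol and SAP*

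**What the plan says.** Study Design and Population excludes people with conditions that would be "contraindications for a weight management intervention, including eating disorders, pregnancy, cancer, or medications that affect body weight".

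Safety protocols and unanticipated outcomes looks ahead to the trial itself: "Possible adverse outcomes may include concerns related to mental health, including eating disorders". It says that the research assistants and the physician co-investigator "are equipped to assess the situation and provide necessary referrals", that difficult feelings can be taken up within the motivational interviews, that campus medical and counselling services are open to all students, and that safety protocols apply when self-harm or harm to others is raised.

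Timing of Visits, Intervention and Control Groups says that, for this feasibility study, a priori "criteria for the discontinuation or modification of the allocated intervention are not available".

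Measurement of Outcomes gives every participant a tracker to wear throughout and asks for a monthly weigh-in at the study office: "They will be asked to weigh themselves monthly and reminders will be sent by email or text message".

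Consent and Ethics adds: "Participants may choose to withdraw from the study at any time and when possible, we will capture the reasons for withdrawal". Data collection and management adds: "We will continue to collect data from participants if they deviate from protocol unless there is withdrawal from the study".

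**The concern.** The plan identifies a group that should not receive this intervention and foresees that a participant may come to belong to it. It then sets no rule for that event. The reason given is that this is a feasibility study. That is a fair reason to have no efficacy-based stopping rule, but an eating disorder is already on the plan's own list of contraindications, so no pilot data are needed to act on it.

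Participant safety is at stake. Unless someone intervenes, a participant who develops an eating disorder stays on a schedule of prompted weighing and activity tracking and, in the intervention arm, of behaviour-change interviews. Someone in that position may not ask to stop. Without a rule, staff must improvise, and in an open-label trial their handling may differ between participants and between arms.

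**Working it through.** **1. The plan's own figure.** Sample size gives 110 participants (55 per arm) from 80% completion, a 7.5% margin and 95% confidence. The formula is n = z²p(1−p)/d² = 1.96² × 0.80 × 0.20 / 0.075² = 109.27, rounded up to 110. It reproduces. It is used below only as the number at risk; the point does not depend on it.

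**2. Would any provision pause exposure after an eating disorder emerges?**

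| Provision (section) | Trigger | Pauses interviews? | Pauses weigh-ins, reminders, tracker? |
|---|---|---|---|
| Exclusion list (Study Design and Population) | Before enrolment only | No | No |
| Discontinuation or modification criteria (Timing of Visits) | None set a priori | No | Not addressed; the sentence covers only the allocated intervention |
| Assess and refer (Safety protocols) | A concern arises | Not stated | Not stated |
| Handling within interviews (Safety protocols) | A concern arises | No, interviews continue | No |
| Safety protocols (same section) | Self-harm or harm to others | Content not given | Content not given |
| Withdrawal (Consent and Ethics) | Participant's choice | Yes, if chosen | Yes, if chosen |
| Data collection after deviation (Data collection and management) | Deviation from protocol | No | No, collection continues |

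The only row that certainly stops exposure depends on the participant asking.

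**3. Remaining exposure, by example.** There are 7 interviews: baseline and months 1 to 6. If a disorder comes to light just after the month 2 contacts, 7 − 3 = 4 interviews remain in the intervention arm. In both arms, 4 monthly weigh-ins (months 3 to 6) and 4 months of tracker wear remain.

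**4. How likely is a case?** The documents give no incidence, so p below is an assumed 6-month risk. Chance of at least one case = 1 − (1 − p)^n.

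| p (assumed) | Expected cases in 110 | At least one in 110 | At least one in 55 (one arm) |
|---|---|---|---|
| 0.5% | 0.55 | 42% | 24% |
| 1% | 1.1 | 67% | 43% |
| 2% | 2.2 | 89% | 67% |
| 5% | 5.5 | 99.6% | 94% |

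Across this range the event would be uncommon for any one participant, but it is plausible enough in the trial as a whole that staff should know in advance what to do.

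**The case against.** The best case for the plan is that its statements are compatible. Only a priori criteria are said to be lacking, and only for the allocated intervention. Weigh-ins and trackers are outcome measurement, which that sentence does not govern. A physician co-investigator can assess and refer, so ad hoc stopping remains open. The Conclusions describe goals chosen by the participant, which may concern sleep, mental health or time management, so interviews can move away from weight without a formal modification. There is also some monitoring: a repeated body-satisfaction item, questions on medication and healthcare use, capture of withdrawal reasons where possible, and recording of protocol deviations.

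Most of this stands. A reader might infer that the plan contradicts itself, or that it obliges staff to keep prompting an affected participant. The text supports neither: it leaves the matter to judgement. What remains is narrower. No sentence tells staff to pause anything, the explicit statement on the intervention confirms that no criterion exists, and the measurement procedures carry no pause rule of their own. Moving an interview away from weight does nothing about weigh-in prompts, and control participants have no interviews. None of the monitoring items described is tied to an action.

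A reader might also infer that every exclusion condition should stop all procedures. Entry exclusions need not be discontinuation criteria. Halting weigh-ins for pregnancy, cancer or any weight-affecting drug would lose outcome data for little gain in safety.

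**Conclusion.** The point holds as a safety gap specific to eating disorders, in both arms. It is worth correcting but does not undermine the trial, because referral, withdrawal and clinical judgement already provide partial protection. How often it would matter rests on assumed incidence; the gap itself rests on the text alone.

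A reader might go further and argue that weight changes from new conditions would distort the BMI variability carried forward, since Sample size promises "estimates of effect size variability that will inform the sample size calculation of a larger definitive trial". The documents do not support that. They give neither an SD nor the size of any such change. Assume 44 completers per arm (80% of 55) and one affected participant whose BMI changes by 3 to 5 kg/m². Pooled variance then rises 9% to 27% if the SD among the others is 1.0, and 3% to 11% if it is 1.5. With 2 × 43 = 86 degrees of freedom, the 95% interval for a variance under normality is about 0.76 to 1.38 times the estimate, so even the largest of these rises lies within sampling error. Intention-to-treat also properly keeps those weights, and a definitive trial analysed in the same way would include such participants. The sample-size argument should not be made.

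**What to change.** Replace the sentence on unavailable criteria in Timing of Visits, Intervention and Control Groups with a rule such as:

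> If an eating disorder is disclosed or suspected after randomization, in either arm, weigh-in requests, reminders, tracker wear and interviews pause until the physician co-investigator has assessed the participant and decides whether they resume. Surveys continue unless the participant withdraws. The event, date and arm are recorded and reported as N, % by arm.

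For new pregnancy, cancer or weight-affecting medication, add that the physician co-investigator decides whether interviews continue, the date is recorded, and weights stay in the intention-to-treat summary.

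**Cost.** A short protocol change, one REDCap form (event, date, arm) and a short ethics amendment. No new visit or staff role is needed.

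**Downsides.** Some 6-month weights may be missing and will count against data completion. Each is 1/110 = 0.9 percentage points of the planned 6-month weights, or 1/55 = 1.8 points within an arm. If every case lost that weight, the assumed 2% risk would cost 2.2/110 = 2.0 points. Detection may also be higher in the intervention arm, because only that arm has monthly interviews. Report safety pauses by arm, so that missing or imputed weights arising from them can be seen and are not mistaken for poor adherence.
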